C) This would be a randomized, double-blind, placebo controlled trial. 1/2 of the patients would receive intra-operative secretin, the other half would receive saline placebo. Both the surgeon and patient would be blinded to the randomization assignment. The advantage of giving secretin would be that it may allow for the identification of a leak intra-operatively and subsequently allow for repair if the leak was identified prior to abdominal wall closure. While the safety profile of the drug is excellent, receiving the medication could theoretically cause an increased intraductal pressure which may cause a leak when one was not already present.

D) Human subjects are needed to evaluate intra-operative, intravenous secretin in patients undergoing pancreatic duct resection.

4. Design, procedures, materials and methods:

Use a level of detail similar to what would be used when submitting an article for publication in a peer reviewed journal. Explain the study procedures, data collection, and analysis process. Please define terms and explain concepts which might be confusing to reviewers who are not expert in the area of the study. If a formal protocol for the study exists, page references to the protocol are acceptable.

This study design is a prospective, double-blind, randomized-controlled trial. We will enroll patients in our institution undergoing pancreatic resection to receive either 1) one dose weight-based Secretin to be given once the closure of the pancreatic resection margin is complete 2) saline placebo.

Consent and basic demographics will be garnered by the physician in an office visit once the surgery has been scheduled and consent for the surgery is being obtained. The consent will be validated by the treating surgeon in the pre-procedure area on the day of the surgery.

The patient will undergo the scheduled surgery. Once the pancreatic anastomosis has been deemed acceptable by the attending physician, but prior to abdominal closure, the patient will be randomized to receive either Secretin (0.2 mcg/kg) or saline placebo. The attending surgeon will be blinded to this assignment.

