10 minutes after receiving the Secretin or placebo, the attending surgeon will examine the anastomosis or repaired cut edge of the pancreas to determine if leakage of pancreatic fluid is noted, leak location(s), type (side branch/main duct), color of the fluid and whether any further intervention was performed in an effort to close the leak. Specifics of operative intervention will be documented. The patient will then undergo standard surgical closure of the abdomen.

As is standard of care at DHMC, surgical drains will be placed adjacent to the anastomosis and drain amylase output will be checked on POD #1 through POD#5. Pancreatic leak is defined according to the International Study Group of Pancreatic Fistula (ISGPF) definition as a clinically relevant postoperative pancreatic fistula is now redefined as a drain output of any measurable volume of fluid with an amylase level >3 times the upper limit of institutional normal serum amylase activity, associated with a clinically relevant development/condition related directly to the postoperative pancreatic fistula. Randomization assignments will be revealed once the patient has been discharged from the hospital following their initial surgical intervention. A follow-up visit with the patient two weeks following discharge, will evaluate for any evidence of ongoing pancreatic duct leak.

The patient will also be followed for thirty (30) days after secretin/placebo administration by the research team to assess for a pancreatic leak and sequelae of a leak, - intra abdominal deep soft tissue infection, surgical site infection, hemorrhage, IR (interventional radiology) drain placement, or reoperation. This will be accomplished by telephone and/or by chart review Patients discharge date will be followed for the study. If no secretin/placebo is administered, the patient will not be followed on the study.

If any of the above are noted during the 30 days following secretin/placebo administration the following will be used to assess causality:

Causality

The following 4-point scale will be used for rating the causal relationship of the AE to the investigational product:

Unrelated: Clearly and incontrovertibly due to extraneous causes, and does not meet criteria listed under unlikely, possible, or probable.

- Unlikely:** Does not follow a reasonable temporal sequence from administration. May have been produced by the patient's clinical state or by environmental factors or other therapies administered.

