- Possible:** Follows as reasonable temporal sequence from administration. May have been produced by the patient's clinical state or by environmental factors or other therapies administered.
- Probable:** Clear-cut temporal association with improvement or cessation of test drug or reduction in dose. Reappears upon re-challenge. Follows a known pattern or response to test drug.

The primary outcome of interest will be the presence of pancreatic leaks based on the amount of drain amylase on or after POD#3. Secondary outcomes will include: 1) technical interventions intraoperatively directed to leak closure or manipulation of the anastomosis following Secretin or placebo stimulation 2) length of stay as a surrogate to complication severity after pancreatic surgery.

Patient demographics, risk factors, operative technique, randomization assignment and outcome data will be recorded on standard case report forms – **See Case Report Forms in Appendix**. Data will be stored in an encrypted hard-drive by a single agent ([name]) who is the only researcher who has access to the randomization data.

5. Inclusion/Exclusion Criteria:

Please provide detailed description of inclusion and exclusion criteria. If a formal protocol for the study exists, page references to the protocol are acceptable.

Inclusion criteria:

1. Scheduled for pancreatic surgery requiring pancreatic resection at DHMC
2. Age greater than 18 years old
3. Ability to provide written informed consent

Exclusion criteria:

1. Inability to provide written informed consent
2. Current ongoing acute pancreatitis
3. Pregnant or nursing mothers
4. Any medical condition which in the judgment of the Investigator renders participation in this study medically inadvisable.
5. Participation in an investigational clinical study for a drug or medical device within 30 days prior to Visit 1.
6. [Any known allergy to methylene blue.](#)

6. Financial Considerations:

Disclosure of financial impact on the participant is critical to informed consent. Insurance cannot be billed for research-related services outside the standard of care or paid for by the funding agency for

the study. The department, the study or the participant may be responsible for payment for research-related services. Participants should know which tests, visits, or procedures will be billed to them or their insurance and which ones will be paid by the funding agency for the study or the department.

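### Assignments are revealed at discharge, before the two-week leak visit, the remaining 30-day follow-up and later causality ratings, and no text keeps those assessors masked

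*Combined protocol and SAP*

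**What the plan says.** Section 3, part C, sets the masking: "Both the surgeon and patient would be blinded to the randomization assignment". Section 4 then says when it ends: "Randomization assignments will be revealed once the patient has been discharged from the hospital following their initial surgical intervention". It does not say to whom the assignment is revealed.

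The same section places further assessment after that point:

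- A clinic visit: "A follow-up visit with the patient two weeks following discharge, will evaluate for any evidence of ongoing pancreatic duct leak".
- Research-team follow-up by telephone or chart review: "The patient will also be followed for thirty (30) days after secretin/placebo administration by the research team to assess for a pancreatic leak". It also covers sequelae: infection, hemorrhage, interventional radiology drain placement and reoperation.
- A rating of any such event: "The following 4-point scale will be used for rating the causal relationship of the AE to the investigational product".

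On the primary outcome, Section 4 says: "The primary outcome of interest will be the presence of pancreatic leaks based on the amount of drain amylase on or after POD#3". The scheduled measurements are early: "drain amylase output will be checked on POD #1 through POD#5". The leak definition in the same section also requires an associated clinically relevant condition.

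On custody, Section 4 says that one researcher alone has access to the randomization data, but it records assignment and outcomes on the same case report forms. Section 14 makes the form available to one person. Section 27(c) limits the stored data to one investigator. Section 7(b) has the primary investigators generate the sequence.

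**The concern.** The trial is described as double-blind, yet the code is opened patient by patient while leak assessment is still under way. A telephone caller, chart reviewer, clinic assessor or causality rater who knows the arm can be influenced on two things: whether a late leak, infection or bleed is called, and whether it is attributed to the study drug.

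This matters because Section 3, part C, accepts that secretin "could theoretically cause an increased intraductal pressure which may cause a leak when one was not already present". Late leaks and their attribution therefore bear directly on the drug's safety. Bias in calls and ratings already recorded cannot be reliably removed at analysis, so it has to be prevented in advance.

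**Working it through.** **1. Order of events and who is masked (Section 4 unless noted)**

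| Step | Timing | Masking stated |
|---|---|---|
| Inspection of the pancreas | 10 minutes after dosing | Surgeon masked |
| Drain amylase | Postoperative days 1 to 5 | Before the reveal for stays longer than 5 days |
| Intraoperative intervention; length of stay (secondary outcomes) | Fixed by discharge | Before the reveal |
| Reveal of assignment | Discharge | Recipient not stated |
| Leak visit | Discharge + 2 weeks | None |
| Leak and sequelae follow-up | To day 30 after dosing | None after discharge |
| Causality rating | Events within 30 days | None |

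On Section 4's timing the leak visit always follows the reveal. The custody statements in Sections 4, 14 and 27(c) concern storage and confidentiality. They do not say that assessors stay masked. A single holder also does not fit with a reveal at discharge, or with a sequence generated by the primary investigators. Nothing separates the holder from outcome assessment.

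**2. Share of the 30 days after the reveal**

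Days exposed = 30 − length of stay. The documents give no length of stay, so it is assumed.

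- 7 days: 30 − 7 = 23 days (77%)
- 10 days: 30 − 10 = 20 days (67%)
- 14 days: 30 − 14 = 16 days (53%)

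**3. The plan's own sample size (Section 7(c))**

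Inputs are 20% v 5%, two-sided alpha 0.05 and 80% power. The mean rate is 0.125.

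- Without continuity correction: n = [1.960·√(2·0.125·0.875) + 0.842·√(0.2·0.8 + 0.05·0.95)]² / 0.15² = 75.1, so 76 per arm.
- With continuity correction: n = (75.1/4)·[1 + √(1 + 4/(75.1·0.15))]² = 87.9, so 88 per arm.

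The stated 88 per arm (176) is reproduced with the correction. It does not bear on the masking point, but it gives the sample size for the next step.

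**4. How far the primary test could be affected**

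Assume a true leak rate of 20% in both arms and 88 per arm. Let *g* be the share of leaks settled only after discharge, and *r* the share of those missed in the secretin arm alone. The recorded secretin rate is then 0.20·(1 − *g·r*), and the bias in the risk difference is 20·*g·r* percentage points. The rejection probability is the exact sum over all tables with two-sided Fisher p ≤ 0.05. Both *g* and *r* are assumptions; the documents give neither.

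| *g* | *r* | *g·r* | Bias (points) | Type I error |
|---|---|---|---|---|
| – | – | 0 | 0 | 3.2% |
| 0.10 | 0.30 | 0.03 | 0.6 | 3.3% |
| 0.30 | 0.30 | 0.09 | 1.8 | 4.0% |
| 0.25 | 0.50 | 0.125 | 2.5 | 4.7% |
| 0.50 | 0.50 | 0.25 | 5.0 | 10.1% |

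The error reaches 5% at *g·r* = 0.1355. Expected leaks per arm are 88·0.20 = 17.6, so this means 17.6·0.1355 = 2.4 leaks missed after the reveal. At *g* = 0.30 it needs *r* = 0.1355/0.30 = 0.45. At *g* = 0.10 it would need *r* = 1.355, which is impossible.

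Over-calling in the placebo arm is not modelled, because an extra leak would still need amylase above three times the upper limit of normal.

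**The case against.** Five points can be made for the plan.

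- **Unmasking of the assessors is inferred.** No recipient is named, and Sections 4 and 27(c) restrict access to one person. If only the custodian or the patient learns the arm, other team members might stay masked. This stands as a limit: the chronology is certain, while exposure of a given assessor is not. The form appendix and consent pages are not in the text and may name a recipient or rater, but they would not change the order of events. A patient who knows the arm can also disclose it by telephone.
- **Attachment B ends participation at discharge, and Section 13 times the clinic visit from the procedure.** On Section 13's timing, the visit would precede the reveal for stays over 14 days. These are real contradictions with Section 4 and need reconciling. Neither supplies masking for the 30-day follow-up.
- **The pressure mechanism would probably show early.** Inspection at 10 minutes and amylase to day 5 are done while masked at all the assumed stays. This stands in part: much of the evidence on a drug-caused leak is protected. Late leaks, infections, hemorrhage and their attribution are not.
- **The causality scale leaves limited room.** Its top level refers to re-challenge, which a single-dose trial cannot readily supply. Reoperation and radiological drain placement are recorded procedures. Both points hold, but the choice between unlikely and possible is still a judgement.
- **No planned test is shown to be affected.** This stands. Both secondary outcomes are fixed by discharge, and the late safety data have no planned hypothesis test.

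**Conclusion.** The concern holds. As written, the plan opens each code before the two-week leak visit in Section 4, the rest of the 30-day leak and sequelae follow-up, and the causality rating of later events, with no provision to mask those assessors. More than half of the 30 days is exposed at each assumed stay (53% to 77%).

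What is at risk is the late safety data. A material effect on the primary p-value is not shown. The primary outcome is reached only when a leak is settled after discharge, either through the assessment window, which has no upper limit, or through the clinical-relevance criterion. Type I error passes 5% only if more than about 13.5% of true secretin-arm leaks are missed after the reveal. This should be fixed because the bias is avoidable and the change is cheap.

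**What to change.** Replace the sentence on revealing assignments with:

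> Assignments stay masked to patients, surgeons, clinic staff and those who assess outcomes at least until that patient's two-week visit, 30-day assessment, leak classification and causality rating are recorded, except for emergency unblinding. Those who generated or hold the randomization list do not make these assessments; other existing research-team members do. The assignment is kept apart from the outcome case report form until they are recorded.

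Then make Sections 4, 7(b), 14 and 27(c) agree on who holds the assignments. Reconcile Section 4, Section 13 and Attachment B on when the two-week visit is timed from and when follow-up ends, because that determines when the hold ends. As a precaution only, with no consequence shown here, staff who enrol or operate should not receive assignments while enrolment is open, because the blocks are small.

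The cost is protocol wording and one staffing condition. If a code holder or sequence generator now does the calls, chart reviews or ratings, another existing team member takes them over, for up to 176 patients. Patients and staff learn the assignment about 16 to 23 days later at assumed stays of 14 to 7 days. No visit, test or patient is added.

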Funding Source (Sponsor): ChiRhoClin, Inc, and ChiRhoClin Research Institute. This is an investigator-initiated project. ChiRhoClin, Inc. will supply the drug, Secretin. [name] will also receive a small grant from the ChiRhoClin Research Institute to support the research coordinator's salary.

1. Abstract.

Provide an abstract of the proposed research in language that can be understood by a non-scientist. The abstract should summarize the objectives of this project and the procedures to be used, with an emphasis on what will happen to the subjects. (Maximum 250 words)

Pancreatic ~~anastomotic~~-leaks complicate pancreatic resection in approximately 20% of cases. The pancreatic anastomosis or repair has been referred to as the Achilles heel of pancreatic surgery. Unfortunately, despite recognition of this problem and multiple operative techniques proposed to prevent this complication, leaks continue to represent a major cause of morbidity for patients undergoing pancreatic surgery. Treatment of leaks often requires nutritional support with total parenteral nutrition to diminish the leak in addition to invasive interventions to contain the leak with drains, stents or in severe cases, reoperation. Experiential data suggest that intra-operative infusions of secretin, a naturally occurring hormone that stimulates bicarbonate release from the pancreas, following resection but just prior to abdomen closure, may identify a leak if present. If secretin can demonstrate evidence of leaking intra-operatively, the pancreatic duct leak may be able to be fixed prior to abdominal closure. We aim to determine if giving an intra-operative infusion of secretin will allow for identification and treatment of leaks after pancreatic reconstruction and prior to abdominal closure, leading to a reduction in the rate of pancreatic ~~anastomotic~~-leaks requiring intervention. We will perform a double-blind, randomized pilot study of 176 patients undergoing pancreatic resection (pancreaticoduodenectomy and distal pancreatectomy) at Dartmouth-Hitchcock Medical Center. 88 of those patients will receive an intraoperative secretin infusion prior to abdominal closure and 88 will receive a saline placebo. Our primary outcome of interest will be the rate of pancreas duct leaks in each group as measured by the amount of amylase present in the surgical drains on or after post operative day (POD)# 3 following surgery.

2. Objectives & Hypotheses:

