List your research objectives and hypotheses.

We hypothesize that intra-operative, intravenous secretin administration will decrease the rate of pancreatic leaks in patients undergoing pancreatic resection. Our primary objective is to determine if intravenous secretin administration will decrease the amount of pancreatic leaks as defined by the 2016 ISGPS definition of postoperative pancreatic fistula, measured by drain fluid amylase on or after POD#3days following resection. Our secondary objectives are to determine if intra-operative intravenous secretin administration changes the management of the pancreatic resection margin intraoperatively or impacts length of stay (LOS)

3. Introduction:

a) Explain the background of this project so that we will understand why it is important to perform this research project. b) Summarize previously published data and pilot studies. Be sure to include a discussion of any data that do not support the study hypothesis. If a study similar to the one being

proposed has already been completed, explain why the proposed study is necessary. c) For studies designed to compare or evaluate therapies, there should be a statement of the relative advantages or disadvantages of alternative modes of therapy. d) If not obvious, explain why human subjects are necessary. Include references for all published data cited. If a formal protocol for the study exists, page references to the protocol are acceptable.

A) Pancreatic duct leaks represent a major complication of pancreatic resection surgery. With a rate of between 20% even at expert, high-volume centers, this dreaded complication causes significant morbidity for patients with associated increased hospital costs. Treatment of pancreatic duct leaks often requires pancreatic rest with intravenous nutrition, endoscopic placement of pancreatic duct stents, and/or repeat surgical operation to close the leak. Despite many advancements in terms of leak closure techniques (duct to mucosa pancreaticojejunostomy, roux-en-Y reconstruction, devices (automatic staplers/ pledgets/stents) pancreatic leaks continue to be a major problem and pancreatic surgeons continue to search for methods to prevent or diminish the severity of pancreatic leaks.

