Synthetic secretin is FDA approved to diagnose exocrine pancreas dysfunction by the functional secretin stimulated pancreas function test and to facilitate pancreatic duct cannulation during ERCP. It is identical in amino acid sequence to native human secretin.

There has not been any reported adverse drug reaction to human secretin stimulation. Rarely, in over 1000 patients who have undergone Secretin-enhanced pancreatic function tests, there is transient vasodilatory effect resulting in flushing of the face and lips with stable vital signs. Therefore, the risks of administering intravenous secretin are modest as described in the package label.

In doses (800cu SQ bid x 7 days) given in clinical studies greater than those offered in the current study, there were no adverse events reported

Secretin is not known to increase the risk of acute pancreatitis episodes in patients with chronic pancreatitis not presently having an acute pancreatitis attack. No allergic reactions have been reported with secretin in commercial use although the administration of a test dose 0.2 mcg IV is still recommended. No significant hemodynamic effects have been observed following administration of secretin. Otherwise, the risks of administering secretin are modest as described in the package label.

The risk of confidentiality should be low given the case report form will be only available to [name] and will be kept in a locked cabinet. All data will be entered on a password-protected Microsoft Excel spreadsheet. Any statistical analysis will be done with patient study numbers and initials for identification of patient.

15. Risk/Benefit analysis:

Describe why the risks to subjects are reasonable in relation to the anticipated benefits to participants and in relation to the importance of the knowledge that may reasonably be expected to result from the study.

A potential risk reduction of up to 15% for pancreatic duct leaks outweighs the given theoretical risks of one time Secretin administration.

16. Research Setting

a) Is this a multi-center study?

Yes No

If yes: Are you the lead investigator? Yes No *If*

you are NOT the lead investigator:

Name of lead investigator:

Institution where the lead investigator is located:

b) List all sites where research will take place and the CPHS at Dartmouth College is the reviewing IRB (e.g. DHMC Alliance Hospitals, DHMC Clinics, WRJ VAMC):

Dartmouth-Hitchcock Medical Center

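### The 30-day causality rating is tied to leak and five leak sequelae, so the non-leak drug reactions the protocol discusses, and death, have no stated route to being rated

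*Combined protocol and SAP*

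**What the plan says.** Section 4 (Design, procedures, materials and methods) states that patients given secretin or placebo are "followed for thirty (30) days after secretin/placebo administration" by the research team "to assess for a pancreatic leak and sequelae of a leak". The sequelae are then named: "intra abdominal deep soft tissue infection, surgical site infection, hemorrhage, IR (interventional radiology) drain placement, or reoperation". Follow-up is by telephone, chart review or both.

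The causality paragraph opens with its trigger: "If any of the above are noted during the 30 days following secretin/placebo administration". The four-point scale that follows is introduced as rating how an adverse event relates to the investigational product.

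Other sections describe what leaks and the drug may bring:

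- **Leak treatment.** Section 1 says: "Treatment of leaks often requires nutritional support with total parenteral nutrition to diminish the leak". It also mentions drains, stents and, in severe cases, reoperation. Section 3A says treatment "often requires pancreatic rest with intravenous nutrition, endoscopic placement of pancreatic duct stents, and/or repeat surgical operation to close the leak".
- **Drug effects.** Section 14b reports a rare "transient vasodilatory effect resulting in flushing of the face and lips" and discusses allergic reaction, hemodynamic effect and acute pancreatitis. Section 3C raises a theoretical leak caused by higher ductal pressure.
- **Monitoring.** Section 8 gives an interim rule based on duct leaks and names the roles heading the monitoring board. It says nothing about collecting adverse events.

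**The concern.** A causality scale for an investigational product is normally fed by all adverse events. Here its trigger admits only leak and leak complications. Followed as written, an allergic reaction or a fall in blood pressure during the infusion, pancreatitis in the following days, or a death outside the listed categories would not be put to the scale.

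The study is placebo-controlled, runs under an IND (section 30), and gives the drug shortly after the pancreatic closure is completed. Section 3B says this intra-operative use has not been studied prospectively. Randomization offers an unbiased comparison of these events between arms, but only if they are recorded and rated in the same way in both.

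There is also a smaller descriptive gap. The abstract aims at fewer leaks that need intervention, yet two of the interventions the protocol calls common are not among the recorded sequelae.

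**Working it through.** No figure in the plan tests this point, so the check sets the sections side by side.

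| Event | Where the protocol raises it | Among the events followed in section 4? | Stated route to causality rating |
|---|---|---|---|
| Pancreatic leak, including one provoked by the drug | 3C, 4 | Yes | Yes |
| The five named sequelae | 4 | Yes | Yes |
| Parenteral nutrition for a leak | 1, 3A | No | Only through the leak itself |
| Pancreatic duct stent | 1, 3A | No | Only through the leak itself |
| Flushing | 14b (reported, rare) | No | None |
| Allergic reaction | 14b (none reported in commercial use) | No | None |
| Hemodynamic effect | 14b (none significant observed) | No | None |
| Acute pancreatitis | 14b (no known increase in risk); ongoing cases excluded in section 5 | No | None |
| Death | Not named in section 4 | No | None |

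1. **Is the list closed?** It names five sequelae and contains no term such as *including* or *other*. The trigger refers back to it, so its scope is leak plus five sequelae.
2. **Leak treatments.** Sections 1 and 3A name four: drains, stents, nutrition and reoperation. Interventional drain placement and reoperation are listed. Missing: 4 − 2 = 2.
3. **Drug reactions.** Section 14b discusses four non-leak reactions, and none is listed. Adding the drug-induced leak of section 3C gives 4 + 1 = 5 possible drug effects, of which 1 has a route to a rating.
4. **Is the gap closed elsewhere?** Section 8 does not close it. Sections 4 and 10 refer to case report forms in an appendix that is not in the text reviewed, so this remains open.
5. **Does the list feed an endpoint?** Section 4 states the primary outcome through drain amylase on or after day 3, and the regression in section 7b uses amylase above three times the upper limit of normal. The leak definition in section 4 adds a clinically relevant condition but does not confine it to the listed events. Neither secondary outcome, intra-operative intervention or length of stay, uses the list. The sample size of 88 per arm is likewise unaffected.

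**The case against.** The strongest reply has three parts.

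**Leak is itself followed.** A reader might infer that leaks treated only by nutrition or a stent go uncounted. The documents do not support that. Section 4 follows leak first and its sequelae second, so such a patient does have a followed event, and a visit two weeks after discharge also looks for ongoing leak. The primary outcome as restated in section 4 rests on amylase, and nothing prevents leak-driven nutrition or stenting from meeting the clinical condition in the definition. The documents give no rate of nutrition-only or stent-only treatment, so any number of lost leaks would be an assumption with no link to an endpoint. This part stands in full.

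**The drug's main surgical risk is covered.** A reader might also infer that reactions to the drug are never rated. That goes too far: the leak from raised ductal pressure in section 3C is followed and rated. Section 14b raises most of the other reactions in order to say they have not been seen, and calls flushing rare, with stable vital signs. This narrows the point to non-leak events. It does not remove it, because that reassurance comes from function tests, commercial use and other clinical studies, not from prospective intra-operative use.

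**The case report forms may collect more.** That is possible, and it rules out saying that no such data are gathered. It does not alter the trigger in section 4, which as written would leave anything extra on the forms unrated.

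**Conclusion.** The concern holds as a gap in safety reporting. Under section 4 as written, flushing, allergic reaction, hemodynamic effect, acute pancreatitis and death have no stated route to a causality rating, and section 8 does not supply one. Separately, the recorded sequelae omit two of the four leak treatments the protocol names, so they do not fully describe the leaks needing intervention that the abstract aims to reduce.

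The size can be given only as these counts. No effect on the leak rate, the power or any endpoint can be computed, and none is claimed. The conclusion assumes that the list is meant as exhaustive, which its wording supports, and that the case report forms do not override the trigger, which cannot be checked here. The change is worth making because it replaces a restrictive rule at little cost; the primary analysis does not depend on it.

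**What to change.** In section 4:

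- Replace the causality trigger so that the scale applies to any adverse event from infusion to day 30. Expressly include intra-operative flushing, hypotension or allergic reaction, postoperative acute pancreatitis, and death.
- Add parenteral nutrition started for a leak and endoscopic pancreatic stent to the recorded sequelae.
- State that all these events will be tabulated by arm, with the anaesthetic record and the chart review already planned as sources.

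If the case report forms already hold some of these items, a cross-reference is enough for collection, but the trigger still needs rewording.

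The cost is protocol wording, a few form items where they are missing, and a little extra chart abstraction. No visit, test or treatment changes.
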